2.5 Analysis of the primary objective

2.5.1 Primary endpoint

The primary variable is the change from baseline (baseline definition as in [section 2.1.1](#)) to 3 years in the CogState Global Cognitive Composite Score (GCCS). The CogState cognitive test battery includes the following seven tasks:

1. **Detection Test (DET)** – Assesses psychomotor function using the speed (milliseconds) of correct responses in a simple reaction time paradigm
2. **Identification Test (IDT)** – Assesses visual attention using the speed (milliseconds) of correct responses in a simple reaction time paradigm
3. **Continuous Paired Associate Learning (CPAL)** – Assesses visual episodic memory measuring accuracy of performance by the number of errors made over 6 learning trials
4. **One back (ONB)** - Assesses working memory using the speed (milliseconds) of correct responses in a n-back paradigm
5. **International Shopping List Test (ISLT)** – Assesses verbal learning using the accuracy (number of words recalled correctly) of recall in a verbal list learning paradigm
6. **International Shopping List Test – delayed recall (ISLT-DR)** - Assesses verbal memory using the accuracy (number of words recalled correctly) of delayed recall in a verbal list learning paradigm
7. **Groton Maze learning Test (GMLT)** – Assesses executive function using the number of total errors (number of error responses over 5 trials) in a hidden pathway maze learning paradigm

Standardized z-scores for each outcome measure and visit will be calculated using the sample baseline mean and standard deviation of individual tasks as follows:

- $Z_{DET} = - (\text{Log}_{10}(\text{DET}) - \text{baseline mean of } \text{log}_{10}(\text{DET}))/\text{SD of } \text{log}_{10}(\text{baseline DET}),$
- $Z_{IDT} = - (\text{Log}_{10}(\text{IDT}) - \text{baseline mean of } \text{log}_{10}(\text{IDT}))/\text{SD of } \text{log}_{10}(\text{baseline IDT}),$
- $Z_{CPAL} = - (\text{CPAL total errors} - \text{baseline mean of CPAL total errors}/\text{SD of baseline CPAL total errors}),$
- $Z_{ONB} = - (\text{Log}_{10}(\text{ONB}) - \text{baseline mean of } \text{log}_{10}(\text{ONB}))/\text{SD of } \text{log}_{10}(\text{baseline ONB}),$
- $Z_{ISLT} = (\text{ISLT} - \text{baseline mean of ISLT})/\text{SD of baseline ISLT},$
- $Z_{ISLT-DR} = (\text{ISLT-DR} - \text{baseline mean of ISLT-DR})/\text{SD of baseline ISLT-DR},$
- $Z_{GMLT} = - (\text{GMLT} - \text{baseline mean of GMLT})/\text{SD of baseline GMLT}$

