2.5.3 Handling of missing values/censoring/discontinuations

The repeated measure ANCOVA modeling as described in the previous section is based on a direct likelihood method with an assumption of missing at random for the missing data mechanism. That means, missing data, including those from dropouts, will be implicitly predicted based on similar patients. By similar we mean patients with similar baseline covariates, measurement histories and who were randomized to the same treatment arm. Various analyses to assess the sensitivity of the primary analysis results to the MAR assumption are described in [section 2.5.5](#).

Data collected more than three months after patients permanent discontinuation of the study medication will be excluded from analyses in both the Safety and PPS analyses. In addition, data collected after patients starting treatments for AD or cognitive impairment will be excluded from “on-treatment” analyses.

Patients with no post-baseline assessments available will be excluded from the primary analysis. However, these patients will contribute to the imputation model for the missing GCCS scores in the sensitivity analyses.

Table 2-3 Overview of missing data handling in analyses for primary endpoint

Analysis	Analysis Set	Data excluded	Missingness assumption	Analysis method	Time points included	Imputed dataset required?
Estimand: The treatment effect had all patients stayed ‘on-treatment’ for the 3-year planned follow-up duration (Under ‘as-treated’ principle)						
Primary	SAF	Off-treatment (>3 months after last dose) After start of treatment for AD or cognitive impairment	MAR	Repeated measure ANCOVA	Weeks 26, 52, 78, 104, 130 and Week 156	No
Sensitivity to Primary analysis	SAF	Off-treatment (>3 months after last dose) After start of treatment for AD or cognitive impairment	MNAR for missing data due to death, HF hosp., stroke	Tipping point analysis followed by ANCOVA	Baseline, Weeks 26, 52, 78, 104, 130 and Week 156	Yes

	SAF	Off-treatment (>3 months after last dose) After start of treatment for AD or cognitive impairment	MNAR for missing data after starting treatments for AD or cognitive impairment	Tipping point analysis followed by ANCOVA	Baseline, Weeks 26, 52, 78, 104, 130 and Week 156	Yes

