	SAF	Off-treatment (>3 months after last dose) After start of treatment for AD or cognitive impairment	MNAR for missing values due to withdrawal for unknown reasons	Tipping point analysis followed by ANCOVA	Baseline, Weeks 26, 52, 78, 104, 130 and Week 156	Yes
	SAF	Off-treatment (>3 months after last dose) After start of treatment for AD or cognitive impairment	MNAR for missing data after starting treatments for AD or cognitive impairment	Jointly model longitudinal measurements and time to starting treatments for AD or cognitive impairment	Baseline, Weeks 26, 52, 78, 104, 130 and Week 156	No
Estimand: The treatment effect had all patients completed the planned follow-up of 3 years regardless of premature study drug discontinuation (under 'Intention-To-Treat' principle)						
Supportive	FAS	No	MAR	Repeated measure ANCOVA	Weeks 26, 52, 78, 104, 130 and Week 156	No
Sensitivity to supportive analysis	FAS	No	MNAR due to death, HF hosp., stroke	Tipping point analysis followed by ANCOVA	Baseline, Weeks 26, 52, 78, 104, 130 and Week 156	Yes
	FAS	No	MNAR after starting treatments for AD or cognitive impairment	Tipping point analysis followed by ANCOVA	Baseline, Weeks 26, 52, 78, 104, 130 and Week 156	Yes
Estimand: The treatment effect had all patients completed the study treatment as per protocol schedule without major protocol deviations (under 'as treated' principle)						
Supportive	PPS	Off-treatment (>3 months after last dose) After start of treatment for AD or cognitive impairment	MAR	Repeated measure ANCOVA	Weeks 26, 52, 78, 104, 130 and Week 156	No
	PPS2	Off-treatment (>3 months after last dose) After start of treatment for AD or cognitive impairment	MAR	Repeated measure ANCOVA	Weeks 26, 52, 78, 104, 130 and Week 156	No
Estimand: Measure of treatment effect of interest MAR = Missing At Random; MNAR = Missing Not At Random; MI = Multiple Imputation						

Following sections provide more detail on the specifications for supportive and sensitivity analyses on primary endpoint as outlined above.

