2.5.5 Sensitivity analysis

The primary analysis methods are consistent under the assumption of ‘missing at random (MAR)’ for the missingness mechanism. Though this is deemed to be an appropriate choice for the primary analysis, this is an untestable assumption based on the observed data ([CHMP, 2010](#), [National Research Council, 2010](#)). Indeed it is conceivable that censoring, respectively the missing data mechanism (e.g., due to death) may be informative and that the cognitive function decline in patients who died would have been steeper than estimated under the MAR assumption. Thus, the primary analysis would favor the valsartan group in the presence of a reduction in mortality in the LCZ696 group. Alternatively, patients starting medications for treatment of AD or cognitive impairment may have had a steeper decline than estimated under the MAR assumption, if they would have not started the medication.

Due to this uncertainty on the missingness mechanism, the following sensitivity analyses will be performed to investigate the sensitivity of the primary analysis results to the MAR assumption.

Tipping point analysis

First, a tipping point analysis ([Permutt 2016](#)), which falls into the class of pattern mixture models, will be performed to evaluate the MAR assumption for missing data due to death, HF hospitalization and stroke.

This sensitivity analysis assumes that missing data due to death, HF hospitalization and stroke are missing not at random (MNAR). More specifically, it assumes that missing GCCS values due to death, HF hospitalization and stroke could have been worse than those imputed under the MAR assumption. It is implemented in the following steps:

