1. Multiple (e.g. 100) imputations of missing GCCS values under a MAR assumption are generated, resulting in multiple (100) complete data sets. This imputation is based on predicted GCCS values from the fitted repeated measures ANCOVA model for the GCCS values (at baseline, Weeks 26, 52, 78, 104, 130 and Week 156) with treatment, age group (<75, ≥75 years), baseline MMSE status (<28, ≥28), baseline cerebrovascular disease burden, visit and treatment-by-visit interaction as factors having fixed effects assuming a common unstructured covariance matrix among visits between treatment group. SAS proc MI FCS statement is used to impute missing values in the following sequence: factor variables in the increasing order of missing frequency, the GCCS at baseline, Weeks 26, 52, 78, 104, 130 and Week 156.
2. For each completed data set, the imputed GCCS values at a given visit for patients who died, or had a HF hospitalization or stroke since the preceding visit, a penalty factor would be applied to the imputed values to reflect that the MAR approach may have overestimated the missing values, e.g. by assuming the actual GCCS values could be a certain percentage (e.g. 5%) worse than MAR based imputations for discontinuations due to death, HF hospitalization and stroke. If the MAR-imputed GCCS value is positive, the final value will be 95% x the imputed value; if the MAR-imputed GCCS value is negative, the final value will be 105% x the imputed value.
3. The primary analysis model as described above will be fitted to the 100 completed data sets following the application of the penalty factor in step 2 which produces 100 sets of parameter estimates and associated covariance matrices.
4. These 100 sets of parameter estimates are then combined by using Rubin's rules to derive overall estimates and their confidence intervals. In a similar manner to the primary analysis, a standardized effect size estimate (Cohen's d) and 95% CI will also be reported using the pooled SD.

The analysis will be repeated for varying penalty factors in a range between 0 and 50%. It is performed using 'on-treatment' data in the SAF, as done in the primary analysis. Tipping point analyses will be performed separately to assess the sensitivity of the results to MAR assumptions under the following situations:

- for missing data due to censoring at the start of AD and cognitive impairment treatments, including on-treatment data only in the SAF

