3.1 Sample size calculation for the primary endpoint

It is currently estimated that approximately 180 patients per group having data on 3-year planned follow up –

- Would provide at least 80% probability that the 2-sided 95% confidence interval (CI) excludes a standardized effect size (Cohen's d) of 0.3 (or greater) in change in composite z-score of the battery test over 3 years, given that there is no expected difference between two treatments.
- Would provide at least 80% probability that the 2-sided CI excludes 0 (corresponding to $p < 0.05$), if the true effect size is 0.3 or greater (in either direction).

An effect size of 0.3 in Cohen's d corresponds to a margin of $0.3 \times SD$ ($SD =$ standard deviation) on the original scale for the difference between treatments in mean global score change from baseline, and is generally considered as small (Cohen 1988). In a systematic review of studies for health-related quality of life instruments that have reported the minimally important difference (MID), it was found that for the majority of studies the MID estimates were consistently close to $0.5 \times SD$ (Norman et al 2003). In addition, socially accepted benchmarks for conditions that induce cognitive impairment such as low level alcohol intoxication within legal driving limit in most countries (0.05%) are generally associated with declines of 0.3 or higher for psychomotor speed, attention and working memory. Therefore, the sample size of the study was determined to be able to detect (or exclude) effect sizes in the magnitude of 0.3 in Cohen's d with high probability, as it appears to be an appropriate choice to guide the interpretation of the cognitive function results.

In addition, defining the magnitude of the MID using a measure of effect size, rather than a raw difference score has additional advantages:

- Expressing the magnitude of an important difference in scale free units (Cohen's d) allows models of clinically meaningful difference to be based on integration of outcomes from a broad set of studies whose characteristics are relevant to the current study (i.e. magnitude of change in cognition related to amyloid, magnitude of change occurring after heart failure, and magnitude of change related to cardiovascular disease).

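### The GCCS tipping-point penalty is a percentage of a near-zero-centred score with no arm-specific version; arm-specific additive deltas on the same imputations would be cheap and more informative

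*SAP*

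**What the plan says.** **Score.** In SAP 2.5.1, "Standardized z-scores for each outcome measure and visit will be calculated using the sample baseline mean and standard deviation of individual tasks". GCCS is the average of the seven task z-scores, signed so that lower is worse.

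**Tipping-point analysis (SAP 2.5.5).** Step 1 imputes all missing GCCS values under MAR from a model that includes treatment and treatment-by-visit. Step 2 penalises imputed values at a given visit "for patients who died, or had a HF hospitalization or stroke since the preceding visit". The worked example is 5%: "If the MAR-imputed GCCS value is positive, the final value will be 95% x the imputed value", with the factor 1.05 for negative values. Then "The analysis will be repeated for varying penalty factors in a range between 0 and 50" per cent. Step 4 reports Cohen's d and its CI. Separate runs cover the start of AD or cognitive-impairment (AD/CI) treatment and withdrawal for unknown reasons. Arm is not mentioned in the penalty rule.

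**Motive.** The same section argues that deaths may hide steeper decline: "Thus, the primary analysis would favor the valsartan group in the presence of a reduction in mortality in the LCZ696 group".

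**Runs listed.** Table 2-3 has "MNAR for missing data due to death, HF hosp., stroke" for the SAF and "MNAR due to death, HF hosp., stroke" for the FAS. Protocol 9.4.4 treats scores missing after these events as MNAR.

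**Conclusion.** SAP 2.5.2 rests the main conclusion on d (LCZ696 minus valsartan) and its 95% CI at Week 156. SAP 3.1 adds that "the sample size of the study was determined to be able to detect (or exclude) effect sizes in the magnitude of 0.3" in Cohen's d.

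**SUVr.** SAP 2.7.1.1 applies the 2.5.5 procedure to change in SUVr, with penalty factors from 1 to 1.6.

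**The concern.** A percentage penalty makes sense on a scale with a meaningful zero. Here zero is the sample's own baseline mean, so the size of the stress depends on how far a patient happens to lie from that mean, in either direction. Because no arm-specific version is stated, the treatment difference moves only through imbalance in affected shares or in imputed levels.

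The trial was prompted by a possible cognitive harm, so a reader will ask how much worse than MAR the missing LCZ696 values would have to be before -0.3, the LCZ696-worse side of the 0.3 used for sizing, is no longer excluded. The planned grid answers that only indirectly. If LCZ696 has fewer events, the grid moves d in its favour.

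The timing phrase in step 2 could also leave most early deaths at their MAR imputations at Week 156.

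**Working it through.** **1. The plan's own figure.** n per arm = 2 x (1.96 + 0.842)^2 / 0.3^2, about 175. At 180 per arm, SE(d) = sqrt(2/180) = 0.105 and power is about 0.81. Also 520 x 0.7 = 364, against 360 needed. SAP 3.1 reproduces.

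**2. Form of the penalty.** For penalty k the final value is X - k|X|. At k = 50%, X = 0 loses 0; X = +0.6 and X = -0.6 both lose 0.30. This needs no assumption.

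**3. Average size.** Assumed, not in the documents: inter-test correlation 0.3 to 0.5 and mean Week 156 GCCS 0 to -0.4. GCCS SD = sqrt((1 + 6 x rho)/7) = 0.63 to 0.76. The mean penalty at 50% is 0.5 x E|X| = 0.25 to 0.34, and it is under 0.1 for 18-25% of affected patients.

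**4. Effect on d at 50%.** Here every affected patient is taken as penalised at Week 156, and the baseline to Week 156 correlation r is assumed to be 0.5 to 0.9. The SD used is the GCCS SD x sqrt(1 - r^2).
- Equal shares and equal levels: about 0.
- A 5-point imbalance in shares: 0.05 x mean penalty / SD = 0.023 to 0.055.
- Equal 15% shares, imputed levels 0.6 lower on LCZ696: 0.02 to 0.12.

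**5. LCZ696-only additive delta.** Half-width = 1.96 x 0.105 = 0.207, so the room from d = 0 is 0.300 - 0.207 = 0.093. Tipping delta = 0.0934 / affected share:

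| Share affected (assumed) | Delta from d = 0 | Delta from d = -0.05 |
|---|---|---|
| 5% | 1.87 SD | 0.87 SD |
| 10% | 0.93 SD | 0.43 SD |
| 15% | 0.62 SD | 0.29 SD |

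An illustrative simulation used one post-baseline visit, 180 per arm, 15% affected in each arm, GCCS SD 0.65, mean change -0.25, SD of change 0.4, 20 imputations and 400 replicates. The probability that the CI excludes -0.3 was 0.74 under MAR and 0.74 under the common 50% penalty. With LCZ696-only deltas of 0.3, 0.6, 0.9 and 1.2 SD it was 0.56, 0.48, 0.32 and 0.20. With 0.9 SD in both arms it was 0.72.

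**6. Timing.** The visit before Week 156 is Week 130. Read literally, a Week 156 value is penalised only for an event in the last 26 weeks. Step 1 imputes all visits before step 2 acts, so an earlier penalty does not carry forward. If events were spread evenly (assumption), 26/156 = 1/6 of them would count at Week 156. The shifts in step 4 hold only if the penalty applies at every missing visit after the event.

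**7. CI formula.** SAP 2.5.2 scales d by sqrt(1/n1 + 1/n2) but divides the noncentrality limits by sqrt(df). At t = 0 and 180 per arm (df about 358) that gives 1.96/18.9 = 0.104, not 0.207. On that text the point where -0.3 is no longer excluded moves from d = -0.093 to about -0.39.

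**8. SUVr.** The 2.5.5 sign rule lowers values, whereas more amyloid means a higher SUVr. With the mean change 0.03 and SD 0.03 in SAP 3.2 (normality assumed), P(change < 0) = 16%, and a plain factor of 1.6 makes those changes more favourable. Applied instead to absolute SUVr, a factor of 1.6 adds 0.6 x SUVr: 0.3 to 0.9 for an assumed SUVr of 0.5 to 1.5, or 10 to 30 SDs of change.

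**9. Run lists.** Table 2-3 has a FAS run for death, HF hospitalization and stroke that the 2.5.5 list lacks. The list has a FAS run for unknown-reason withdrawal that the table lacks.

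**The case against.** The planned analysis does what it was written to do. Each of the two concerns in SAP 2.5.5 has a tipping-point run, and AD/CI-treatment start also has the joint model. Protocol 9.4.4 asks for no more than imputation analyses of this kind. This stands: the point is an improvement, not a defect in the primary analysis.

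A reader might infer that the grid cannot tip. The documents do not support that: imputation uses treatment, levels can differ by arm, and the top of the 0.02 to 0.12 range exceeds 0.093. A reader might also infer that -0.3 is a non-inferiority margin. None is declared; 0.3 is a magnitude used for sizing and interpretation.

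The SAP's silence on arm does not forbid arm-specific factors, but none is planned. Affected shares are assumed, and 15% would be half of the 30% total loss allowed for in SAP 3.3. In the FAS, scores obtained after a hospitalization or stroke stay as observed, so death is the main gap there. At a 5% share, tipping from d = 0 needs a large shift of 1.87 SD.

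On SUVr, the text does not settle whether the factor multiplies the change or the level. Neither reading works well.

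**Conclusion.** The point holds as a low-cost improvement. It follows from the formula alone that the percentage penalty depends on distance from the baseline mean. It cancels between arms when affected shares and imputed levels are similar. It is a fair test of the mortality argument, but it does not locate where a departure confined to LCZ696 would end the exclusion of -0.3.

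The step 2 timing phrase matters as much as the form of the penalty, because read literally it leaves most follow-up time without effect at Week 156 and differs from Protocol 9.4.4.

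The tipping deltas rest on the assumed shares and a half-width of 0.207, and so on first reconciling the CI formula in SAP 2.5.2. Nothing here implies bias in the primary estimate. The mismatch in FAS runs is editorial.

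**What to change.** Replace step 2 of SAP 2.5.5 with wording such as: for affected patients, subtract delta_arm x SD (the model SD of GCCS change at Week 156) from the imputed values at all missing visits after the event; vary the two arms' deltas separately over a fixed grid, for example 0 to 2 SD in steps of 0.25, including equal deltas and LCZ696 only; report d and its CI for each pair, and mark where the CI stops excluding -0.3 and where its conclusion about 0 changes.

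Equal deltas keep the existing mortality test. Use the same scheme for AD/CI-treatment start and unknown-reason withdrawal. Say that -0.3 is a reference for interpretation, not a margin. Reconcile the scaling of d and its CI in SAP 2.5.2 before reading the grid.

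For SUVr (SAP 2.7.1.1), add arm-specific deltas to the imputed change in the higher direction, for example in steps of 0.005. Make Table 2-3 and the 2.5.5 list agree on the FAS runs.

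Cost: SAP wording and one changed post-imputation step, with the same imputations and Rubin's-rules code. The downside is a larger results grid.

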2.5.2 Statistical hypothesis, model, and method of analysis

The change from baseline in the GCCS of CogState test battery will be analyzed using a repeated measures analysis of covariance (ANCOVA) model in which treatment, age stratification factor, MMSE stratification factor, education level, APOE4 status (carrier vs. non-carrier), baseline cerebrovascular disease burden, visit (Weeks 26, 52, 78, 104, 130 and Week 156) and treatment-by-visit interaction are included as fixed-effect factors and baseline GCCS and visit-by-baseline GCCS interaction as covariates, with a common unstructured covariance matrix among visits between treatment groups. The adjusted mean changes at 3 years (Week 156) within each treatment, the difference in mean changes at 3 years (Week 156) between the two treatments, and its 95% confidence interval obtained from the above model will be presented. In addition, the treatment difference (LCZ696-valsartan) in mean changes from baseline to 3 years will also be expressed based on a standardized effect size (Cohen's d) with a 2-sided 95% confidence interval. The Cohen's d will be estimated by using the adjusted between-treatment mean difference, divided by the estimated pooled standard deviation. The estimated standard deviation for the mean difference is:

$$SD = \left(\frac{1}{n_1} + \frac{1}{n_2} \right)^{1/2} \hat{\sigma}$$

where n1 and n2 are the number of patients within each treatment group and $\hat{\sigma}$ is the pooled standard deviation of the within treatment group adjusted mean change. Cohen's d can be rewritten in terms of t value of the estimated between treatment group difference based on the adjusted mean changes from the model mentioned above:

$$t = \frac{\hat{\mu}_1 - \hat{\mu}_2}{SD} = \frac{\hat{\mu}_1 - \hat{\mu}_2}{\left(\frac{1}{n_1} + \frac{1}{n_2} \right)^{1/2} \hat{\sigma}}$$

$$\hat{d} = \frac{\hat{\mu}_1 - \hat{\mu}_2}{\hat{\sigma}} = \left(\frac{1}{n_1} + \frac{1}{n_2} \right)^{1/2} \times t$$

Confidence interval (CI) of Cohen's d is based on 95% CI of the noncentrality parameter of t value divided by the square root of the degrees of freedom from the estimated between treatment group adjusted mean change (Cumming and Finch 2001). The analysis is based on a direct likelihood method with an assumption of missing at random (MAR) for the missing data mechanism.

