- for missing data due to withdrawal for unknown reasons, including on-treatment data only in the SAF
- for missing data due to censoring at the start of AD and cognitive impairment treatments, including all data in the FAS
- for missing data due to withdrawal for unknown reasons, including all data in the FAS

In a similar procedure, missing values due to respective reasons will be imputed assuming MNAR while assuming all other missingness mechanism to be MAR.

If model convergence issue arises in the tipping point analysis, the model in step 1 above will be modified by replacing the common unstructured covariance matrix with a compound symmetry covariance matrix between treatment groups. If convergence issue remains after implementing the compound symmetry covariance matrix, the model will be simplified by removing baseline cerebrovascular disease burden as explanatory factor from the model.

Joint model approach

To adjust for the non-ignorable missingness in the primary endpoint due to starting AD/CI related medication, a joint modeling of the primary longitudinal process and missingness mechanism will be performed using a shared parameter approach (Vonesh et al 2006). Specifically, a generalized linear mixed model (GLMM) for the longitudinal GCCS outcome and a Cox proportional hazard model for the time to starting AD/CI related medication will be fitted which share common unobserved patient-specific random effect. It is assumed that the longitudinal outcome process is independent of the time to starting AD/CI related medication conditional on the random effects.

Model for longitudinal outcomes

The repeated GCCS outcomes will be analyzed following a repeated measures ANCOVA model with treatment, age stratification factor, MMSE stratification factor, education level, baseline cerebrovascular disease burden, APOE4 status (carrier vs. non-carrier) are included as factors and baseline GCCS, assessment time (in days), assessment time by baseline GCCS and assessment time by treatment interaction as covariates having fixed effects. Further, a patient-specific random intercept and random slope (on time) is fitted to the model. In general, the model has the following mathematical form:

$$y_i(t) = m_i(t) + e_i(t)$$
$$m_i(t) = X_i^T(t)\beta + (b_{0i} + b_{1i}t)$$

where

$y_i(t)$ =GCCS outcome for i-th patient at time t (assessment time in months)

$m_i(t)$ = 'True' (unobserved) patient-specific mean GCCS outcome for i-th patient at time t

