$X_i(t)$ = Covariate vector having fixed effects on mean GCCS outcome for i-th patient (treatment, age stratification factor, MMSE stratification factor, education level, baseline

cerebrovascular disease burden, APOE4 status, baseline GCCS, assessment time, assessment time by baseline GCCS and assessment time by treatment)

β = Parameter vector representing fixed effects of covariate vector $X_i(t)$ on mean GCCS outcome at time t

b_{0i} =Patient-specific random intercept

b_{1i} =Patient-specific random slope on time

$e_i(t)$ = Measurement error,

Assumption:

- (b_{0i}, b_{1i}) 's are assumed to be following bivariate normal distribution with mean vector 0 and unstructured covariance matrix independently for all patients
- $e_i(t)$'s are assumed to be independently normally distributed with mean vector 0 and an covariance matrix with no correlation between the time points and an common variance σ_e^2 on the diagonal elements

Model for time to starting AD or CI related medication

Time to starting AD or CI related medication from randomization will be calculated as –

- Date of starting AD or CI related medication – Randomization date +1

Patients who do not start AD or CI related medication, their data will be censored at the earlier of –

- Last known date patient took study medication
- Date of withdrawal of consent
- Date of last visit

A exponential regression is fitted to the time to starting AD or CI related medication.

$$\lambda_i(t|H_i(t), X_i) = \lambda_0 \exp(X_i^T \gamma + \alpha m_i(t))$$

where

$\lambda_i(t|H_i(t), X_i)$ =Conditional intensity function at time t for i-th patient given the covariate and history of outcomes until time t, $H_i(t)$

λ_0 =Baseline hazard function that is constant over time

γ = Parameter vector representing fixed effects of time-independent covariate vector X_i on event risk (hazard) at time t

α =Fixed effect of ‘true’ patient-specific mean outcome at time t

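### Table 2-3 and the text of SAP 2.5.5 together make baseline GCCS both an outcome row and a covariate in the joint-model sensitivity analysis

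*SAP*

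**What the plan says.** SAP 2.5.3, Table 2-3, gives the time points included in each analysis of the primary endpoint. For the row "Jointly model longitudinal measurements and time to starting treatments for AD or cognitive impairment" the entry is "Baseline, Weeks 26, 52, 78, 104, 130 and Week 156", and no imputed data set is required. For the primary analysis the entry is "Weeks 26, 52, 78, 104, 130 and Week 156".

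The primary model (SAP 2.5.2) has "baseline GCCS and visit-by-baseline GCCS interaction as covariates". The joint model (SAP 2.5.5) has the same kind of adjustment. Its text reads "The repeated GCCS outcomes will be analyzed following a repeated measures ANCOVA model", with "baseline GCCS, assessment time (in days), assessment time by baseline GCCS and assessment time by treatment interaction as covariates having fixed effects". The outcome y_i(t) is the GCCS value itself, not the change from baseline. In addition, "a patient-specific random intercept and random slope (on time) is fitted to the model", and the measurement errors have a "covariance matrix with no correlation between the time points and an common variance". The hazard of starting AD or cognitive-impairment medication depends on the patient's fitted mean m_i(t). The text of 2.5.5 does not list the visits that count as outcomes.

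**The concern.** In the primary row, baseline GCCS is a covariate and Baseline is absent from the time points. The FAS, PPS and PPS2 rows follow the same pattern, so the column appears to list outcome times. The tipping-point rows do list Baseline, but their imputation model treats baseline GCCS as one of the outcomes. The joint model has no imputation step, so that reason does not apply to it. A programmer who follows both table and text would include a t = 0 outcome row while baseline GCCS and its time interaction sit on the right-hand side.

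At t = 0 the outcome would then equal a covariate exactly, for every patient. A model with one error variance at all times cannot represent a row without error, so the misfit has to go into the baseline coefficients and the random effects. The treatment effect is also pinned near zero at t = 0. This is the one planned analysis that models GCCS jointly with the start of AD or cognitive-impairment medication. If it differed from the primary result, readers would blame informative censoring when the cause could be the extra row.

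**Working it through.** **The plan's figures.** The documents give no variance component or expected result for the joint model. The sample size sets the scale: 2 × (1.960 + 0.842)² / 0.3² = 174.5, so 175 per group against the stated 180, and 360 / 0.70 = 514.3, so 515 against the stated 520. The simulations used 520 patients, 260 per arm.

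**Hand check, complete data, outcomes at 0, 0.5, ..., 3 years.** Assume intercept variance 0.40 and error variance 0.10.
- After baseline, the coefficient on baseline GCCS should be 0.40 / (0.40 + 0.10) = 0.80, with leftover intercept variance 0.40 × (1 − 0.80) = 0.08.
- At t = 0 the coefficient is exactly 1, with no leftover variance.
- The mean time is 1.5 and the sum of squares about it is 2 × (1.5² + 1² + 0.5²) = 7. A straight line through 1, 0.80, ..., 0.80 has slope −1.5 × 0.20 / 7 = −0.043 per year and intercept 0.829 + 1.5 × 0.043 = 0.893. Simulation with complete data gave −0.043 and 0.890.
- For a treatment effect δ constant from Week 26 and zero at t = 0, the line has slope 1.5δ / 7 = 0.214δ and mean 6δ / 7 = 0.857δ. At 3 years it gives 0.857δ + 1.5 × 0.214δ = 1.18δ, an overstatement of 18%. Simulation gave 19%.
- An effect that is zero, or linear from zero, lies on the fitted line, so there is no bias.

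**Simulation of the longitudinal part only.** Random intercept and slope, one error variance; covariates treatment, baseline, time, time × baseline, time × treatment. All variances are assumptions.
- A: intercept variance 0.40, slope variance 0.01 per year², error variance 0.10; 30% loss.
- B: intercept SD 0.6, error SD 0.3, slope SD 0.1 per year; about 35% loss.
- C: intercept SD 0.5, error SD 0.4, slope SD 0.1 per year; similar loss.

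In B and C the true 3-year effect is 0.3 SD of change: 0.3 × √(9 × 0.01 + 2 × 0.09) = 0.156 and 0.3 × √(9 × 0.01 + 2 × 0.16) = 0.192. There were 60 to 120 trials per scenario.

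Post-baseline rows only → baseline row added (linear effect in B and C):

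| Quantity | A | B | C |
|---|---|---|---|
| Random intercept | variance 0.079 → 0.012 | SD 0.263 → 0.097 | SD 0.304 → 0.115 |
| Random slope | variance 0.010 → 0.0145 | SD 0.098 → 0.120 | SD 0.094 → 0.127 |
| Baseline coefficient | 0.80 → 0.90 | 0.795 → 0.902 | 0.601 → 0.811 |
| Baseline-by-time, per year | 0 → −0.05 | 0.002 → −0.049 | 0.002 → −0.100 |
| SE, 3-year difference | 0.0456 → 0.0486 | 0.0461 → 0.0491 | 0.0528 → 0.0562 |

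The intercept variance falls by 1 − 0.012 / 0.079 = 85% in A, 1 − (0.097 / 0.263)² = 86% in B and 1 − (0.115 / 0.304)² = 86% in C. The SE rises by 6 to 7%.

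| True effect | Setting | True value | Post-baseline only | Baseline row added |
|---|---|---|---|---|
| Null | B | 0 | −0.004 | −0.006 |
| Linear | A | −0.15 | −0.139 | −0.138 |
| Linear | B | 0.156 | 0.156 | 0.155 |
| Linear | C | 0.192 | 0.182 | 0.182 |
| Constant from Week 26 | A | −0.15 | −0.151 | −0.185 (+23%) |
| Constant from Week 26 | B | 0.156 | 0.152 | 0.186 (+19%) |
| Constant from Week 26 | C | 0.192 | 0.189 | 0.235 (+22%) |
| Plateau at 1 year | B | 0.156 | 0.173 | 0.197 |
| Plateau at 1 year | C | 0.192 | 0.216 | 0.244 |

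Repeat runs of A with the constant effect gave −0.181 to −0.187 (21 to 25% too large). Coverage of the 95% CI for the constant effect was 85 to 92% with the baseline row and 92 to 97% without it, imprecise at these trial numbers. For the plateau, the linear time term alone already overstates by 11 to 12%, and the baseline row adds about 15 points.

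**The other way to remove the double use.** Keeping baseline as an outcome and dropping it as a covariate, in setting A with the constant effect, gave −0.184 to −0.186 and SE 0.066, against SE 0.045 with post-baseline rows only.

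**The case against.** The double use is inferred. Table 2-3 is an overview of missing-data handling, the sections after it are said to carry the detail, and the text of 2.5.5 never says that t = 0 is an outcome. The joint-model cell matches the tipping-point cells above it and may simply be a carry-over. This stands: the certain defect is that table and text do not agree, and the numerical consequences follow only if both are taken literally.

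It is also fair that the bias in the 3-year effect does not come from the duplication as such. It comes from drawing a linear treatment-by-time term through the t = 0 row, and it remains when baseline is removed as a covariate. The variance distortion, the false baseline-by-time slope and the 7% loss of precision do come from the double use.

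A reader might infer that the correction for informative start of AD medication, and so the whole joint-model result, must be wrong. The working does not support that. The hazard model was not fitted. The hazard depends on m_i(t), which contains the fixed part as well as the random effects, so variance moved from the intercept into the baseline coefficient stays inside m_i(t).

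A reader might also infer that the primary result is compromised. It is not, because its own row and model are consistent. Start of AD or cognitive-impairment treatment is also examined by tipping-point analyses in the Safety set and the FAS. Protocol 9.4.4 presents the joint model as exploratory, and SAP 2.5.5 allows its results to be left out of the report if it fails to converge.

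**Conclusion.** The point holds as an inconsistency in one sensitivity analysis that should be corrected before the model is run. Fitted literally, the random-intercept variance falls by about 85%, the slope variance is inflated, a false baseline-by-time slope of about −0.05 per year appears (−0.10 in the noisier setting), and the SE of the 3-year difference rises by about 7%. The 3-year effect is overstated by roughly 20 to 25% if it is already present by Week 26, and no bias is added if it is null or linear.

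The sizes rest on assumed variances, since the documents give none, and on the longitudinal part alone with a reduced covariate list. The effect on the hazard link is unknown. The primary analysis is unaffected.

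**What to change.** Delete Baseline from the joint-model row of Table 2-3. State in SAP 2.5.5 that the longitudinal outcomes are GCCS at Weeks 26, 52, 78, 104, 130 and 156, with baseline GCCS as covariate, as in the primary model. The cost is one table edit and one sentence. Baseline information is kept through the covariate.

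Do not instead keep baseline as an outcome and drop it as a covariate. That leaves the same bias for an effect that is not linear from zero and raises the SE by about 45% over the post-baseline model (0.066 / 0.045 = 1.47; 0.067 / 0.0458 = 1.46 in a repeat run).

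In the same edit, settle the unit of assessment time, which 2.5.5 gives in days in one place and in months in another.
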